3.5.3 Other Co-Variates/Control Variables

Baseline demographics and clinical characteristics will be used in statistical analysis models.

3.5.4 Derived Variables

- Number of consultations/visits to healthcare professionals for treatment of RA, categorized by the treatment department
 - ✓ Family Medicine
 - ✓ Rheumatologist
 - ✓ Gerontologist
 - ✓ Orthopedist
 - ✓ Internist
 - ✓ Emergency department
 - ✓ Traditional Medicine
 - ✓ Rehabilitation Medicine
 - ✓ Other
- Number of procedures received when visiting the healthcare professional(s) for treatment of RA
 - ✓ Chest X-Ray
 - ✓ Spine X-Ray
 - ✓ Neck X-Ray
 - ✓ Shoulder X-Ray
 - ✓ Hand X-Ray
 - ✓ Knee X-Ray
 - ✓ MRI
 - ✓ CT scan
 - ✓ Electrocardiogram
 - ✓ Blood sample taken
 - ✓ Urine test
 - ✓ Endoscopy
 - ✓ Bone scan
 - ✓ Liver function test
 - ✓ Tuberculin Skin Test
 - ✓ Sputum tests
 - ✓ Other

- Number of surgeries received when visiting the healthcare professional(s) for treatment of RA
 - ✓ Arthroscopy
 - ✓ Carpal tunnel release
 - ✓ Cervical spinal fusion
 - ✓ Total knee replacement
 - ✓ Total hip replacement
 - ✓ Knee arthrodesis (fusion)
 - ✓ Hip arthrodesis (fusion)
 - ✓ Synovectomy
 - ✓ Other
- Number of hospitalizations in relation to RA
- Length of stay: total days in hospital in relation to RA
- Number of concomitant medications taken for RA
- Disease Modifying Antirheumatic Drug (DMARD)
 - ✓ Auranofin (Ridaura, Myochrysine)
 - ✓ Azathioprine (Imuran)
 - ✓ Cyclosporine (Sandimmune and Neoral)
 - ✓ Hydroxychloroquine (Plaquenil)
 - ✓ Leflunomide (Arava)
 - ✓ Methotrexate (Rheumatrex, Folex)
 - ✓ Minocycline (Minocin, Dynacin and Vectrin)
 - ✓ Sulfasalazine (Azulfidine)
 - ✓ Others
- Anti-inflammatory Drug (NSAID)
 - ✓ Ibuprofen (Advil, Motrin, Nuprin)
 - ✓ Naproxen (Naprosyn, Anaprox, Aleve)
 - ✓ Celecoxib (Celebrex)
 - ✓ Aspirin (ASA)
 - ✓ Diclofenac (Voltaren)
 - ✓ Indomethacin (Indocid)
 - ✓ Others
- Others
 - ✓ Steroids
 - ✓ Stomach or gastric medications

3.5.5 Conventions

Given the real world nature of the data, multiple imputation methods for missing data will introduce bias as missing data cannot be considered completely at random (MCAR) or at random (MAR). Due to the observational nature of this study, non-imputing process will be applied, except with date data where the exact day is missing; day “15” will be assumed. Efficacy measures are not assessed after a participant discontinues adalimumab. The exception to this will be the analysis of proportion of patients at 24 weeks who remain on adalimumab. Item level data on the PROs will be imputed according to the developers’ recommendations. Therefore, the analysis will be based on available data. The number of patients with missing data for each variable will be summarized and reported.

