9.1.1 Schedule of Events

Table 1 Data Collection/Observation

	Data Collection/Observation	Baseline ^a ± 7 days	Week 12 (V2) ± 7 days	Week 24 (V3) ± 7 days	Early Termination / Drop out	70 days after the Week 24 or the last dose	150 days after the Week 24 or the last dose
Clinician Packet	Inclusion/exclusion form	X					
	Clinical history/patient demographics	X					
	Comorbidities	X					
	DAS28 (ESR) or DAS28 (CRP)	X	X	X	X		
Patient Packet	EuroQoL 5-Dimension (EQ-5D)	X	X	X	X		
	Short Form 36-Item Health Survey (SF-36)	X	X	X	X		
	Health Assessment Questionnaire (HAQ)	X	X	X	X		
	Work Productivity and Activity Impairment Questionnaire (WPAI)	X	X	X	X		
	Healthcare Resource Utilization (HCRU)	X	X	X	X		
	Patient Global Impression of Change (PGIC)		X	X	X		
	Patient Treatment Satisfaction Questions	X	X	X	X		
Clinicia	Adverse events	←				→	
	Pregnancy	←				→	

a. The Baseline will serve as the reference date for all subsequent time-points. A ± 7 day window is permitted around scheduled data collection time-points.

9.2

Setting

The study will take place in single country (Taiwan) with multiple centers. The study sites will be identified and selected by AbbVie. The study population shall comprise of male and/or female patients who are attending a routine clinical visit and meet all of the inclusion criteria and none of the exclusion criteria. Overall, approximately 100 subjects with clinically diagnosed RA are planned to be enrolled in the study at up to 7 sites.

The recruiting investigators will select potentially eligible patients from consecutive visits within their clinic based on the inclusion and exclusion criteria (Section 9.2.1 and Section 9.2.2). It is the responsibility of each physician to ask every consecutive patient who meets the inclusion criteria of the study to participate to avoid selection bias, and if investigators hold different types of clinics (e.g. routine visit clinics versus emergency clinics), only patients visiting their routine clinics will be used for patient selection.

Site personnel should thoroughly assess the eligibility criteria and evidence of this should be stored with the source documentation at site. Where there is any deviation from the inclusion/exclusion criteria, the patient should be excluded from the study.

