Subjects that initially screen fail for the study may be permitted to re-screen following re-consent. All screening procedures with the possible exceptions noted below will be repeated. The subject must meet all inclusion and none of the exclusion criteria at the time of re-screening in order to qualify for the study. There is no minimum period of time a subject must wait to re-screen for the study. If the subject had a complete record of eligible criteria including a PPD test (or equivalent), or Interferon-Gamma Release Assay (IGRA; QuantiFERON-TB Gold In-Tube test or T-SPOT TB test), Chest x-ray (if applicable) and ECG no more than 3 months (90 days) have passed, these data will not be required to be repeatedly collected for re-screening. As appropriate, sites are encouraged to contact the AbbVie Medical Monitor to confirm if subjects should or should not be re-screened.

9.2.1 Inclusion Criteria:

Patients meeting all of the following inclusion criteria at baseline will be included:

1. Subject has a diagnosis of RA as defined by the 1987 revised ACR classification criteria and/or the ACR/ the European League against Rheumatism (EULAR) 2010 classification criteria (any duration since diagnosis)
2. Male or female subjects ≥ 18 years of age (local definition according to adalimumab label) who is in compliance with eligibility for adalimumab based on the local label
3. Patients with moderate to severe RA defined as DAS28 (ESR) or DAS28 (CRP) > 3.2

4. Biologically treatment naïve and initiated adalimumab at baseline visit
5. Availability of clinical data of the previous 12 weeks prior to baseline
6. Ability to self-complete patient questionnaires
7. Subject must be able and willing to provide written informed consent and comply with the requirements of this study protocol

Additional Inclusion Criteria

8. Female subjects who are either not of childbearing potential, defined as postmenopausal for at least 1 year or surgically sterile (bilateral tubal ligation, bilateral oophorectomy and/or hysterectomy) or are of childbearing potential and are practicing an approved method of birth control throughout the study and for 150 days after the Week 24 dosing or the last dose of adalimumab.

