9.2.6 Removal of Subjects from Therapy or Assessment

1. Discontinuation of Individual Subjects

A subject may withdraw from the study at any time. The Investigator may discontinue any subject's participation for any reason, including an adverse event, safety concerns or failure to comply with the protocol.

Subjects will be withdrawn from the study immediately if any one of the following occurs:

- Clinically significant abnormal laboratory result(s) or adverse event(s), as determined by the Investigator in consultation with the AbbVie Medical Monitor.
- The Investigator believes it is in the best interest of the subject.
- The subject requests withdrawal from the study.
- Inclusion and exclusion criteria violation was noted after the subject started study drug, when continuation of the study drug would place the subject at risk as determined by the AbbVie Medical Monitor (see *Section 5.2* and *Section 7.0*).
- Introduction of prohibited medications or dosages when continuation of adalimumab would place the subject at risk as determined by the AbbVie Medical Monitor.
- Subject is non-compliant with TB prophylaxis.
- The subject becomes pregnant during the study period.
- Subject has dysplasia of the gastrointestinal tract or a malignancy, except for localized non-melanoma skin cancer. Discontinuation for carcinoma in-situ of the cervix is at the discretion of the Investigator.
- Subject is diagnosed with lupus-like syndrome, multiple sclerosis or demyelinating disease.
- Subject is significantly non-compliant with clinical follow-up which would put the subject at risk for continued participation in the trial, as determined by the Investigator, in consultation with the AbbVie Medical Monitor.

The subject will be treated in accordance with the Investigator's best clinical judgment. If the subject prematurely dropped out from the study, the pre-defined Terminal Visit data should be collected within 2 weeks of the last dose of adalimumab, and preferably prior to the initiation of another therapy. However, these data collection should not interfere with the initiation of any new treatments or therapeutic modalities that the Investigator feels are necessary to treat the subject's condition. A final data of a subject will be recorded

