9.7.7 Safety Analysis

Adverse events occurring while participants are on adalimumab will be coded using Common Terminology Criteria for Adverse Events (CTCAE) classification individually listed by indication groups. The incidences and percentages of individuals experiencing AEs and SAEs within each indication will be summarized by System Organ Class (SOC) with further summaries by severity and relatedness (causality) categories. Adverse events leading to discontinuation and concomitant medications will also be listed and summarized.

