1. Arthroscopy 2. Carpal tunnel release 3. Cervical spinal fusion 4. Total knee replacement 5. Total hip replacement 6. Knee arthrodesis (fusion) 7. Hip arthrodesis (fusion) 8. Synovectomy 9. Other: _____			

* For day surgeries, please input 0 days.

6. Please check any Hylan G-F 20 (Synvisc) injections this patient has received for her/his Rheumatoid Arthritis since the last completed survey.			
 No injection performed			
 Yes →	Injection Place	Dosage	Number of shots
	 1 Hip	_____ ml	_____
	 2 Knee	_____ ml	_____

1023259 Real-World Impact of RA

			-			
Site number	Participant ID					

7. Please check any adalimumab (Humira) injection this patient has received for her/his Rheumatoid Arthritis since the last completed survey.						
 No, no injection performed		Dosage	Number of Times			
 Yes →			_____ mg	_____		
Administration stop date (if stopped)		____/____/____ (DD/MM/YYYY)				

1023259 Real World Impact of RA
[Site number] - [Participant ID]

8. Please record all of the medications this patient has received for her/his Rheumatoid Arthritis since the last completed survey			
Drug Name	Average number of pills per day	Dose strength	Times per month
Disease Modifying Antirheumatic Drug (DMARD)			
 ₁ Auranofin (Ridaura, Myochrysine)	_____	_____ mg	_____
 ₂ Azathioprine (Imuran)	_____	_____ mg	_____
 ₃ Cyclosporine (Sandimmune and Neoral)	_____	_____ mg	_____
 ₄ Hydroxychloroquine (Plaquenil)	_____	_____ mg	_____
 ₅ Leflunomide (Arava)	_____	_____ mg	_____
 ₆ Methotrexate (Rheumatrex, Folex)	_____	_____ mg	_____
 ₇ Minocycline (Minocin, Dynacin and Vectrin)	_____	_____ mg	_____
 ₈ Sulfasalazine (Azulfidine)	_____	_____ mg	_____
 ₉ Others	_____	_____ mg	_____
Anti-inflammatory Drug (NSAID)			
 ₁₀ Ibuprofen (Advil, Motrin, Nuprin)	_____	_____ mg	_____
 ₁₁ Naproxen (Naprosyn, Anaprox, Aleve)	_____	_____ mg	_____
 ₁₂ Celecoxib (Celebrex)	_____	_____ mg	_____
 ₁₃ Aspirin (ASA)	_____	_____ mg	_____
 ₁₄ Diclofenac (Voltaren)	_____	_____ mg	_____

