 ₄ Shoulder X-Ray _____ times
 ₅ Hand X-Ray _____ times
 ₆ Knee X-Ray _____ times
 ₇ MRI _____ times
 ₈ CT scan _____ times
 ₉ Electrocardiogram _____ times
 ₁₀ Blood sample taken _____ times
 ₁₁ Urine test _____ times
 ₁₂ Endoscopy _____ times
 ₁₃ Bone scan _____ times
 ₁₄ Liver function test _____ times
 ₁₅ Tuberculin Skin Test _____ times
 ₁₆ Sputum tests _____ times
 ₁₇ Other: _____ times

1023259 Real-World Impact of RA
[Site number] - [Participant ID]

3. Since you last filled out this questionnaire, when you visited the healthcare professional(s) for treatment of your rheumatoid arthritis, were there any surgeries performed?

 No, consultation only			
 Yes →	Type of Surgery (Please input the number of the list below)	Length of stay*	Date of surgery (DD/MM/YYYY)
	 1	_____ days	_____/_____/_____
	 2	_____ days	_____/_____/_____
	 3	_____ days	_____/_____/_____
	 4	_____ days	_____/_____/_____
	 5	_____ days	_____/_____/_____

List of common surgeries for rheumatoid arthritis:

1. Arthroscopy
2. Carpal tunnel release
3. Cervical spinal fusion
4. Total knee replacement
5. Total hip replacement
6. Knee arthrodesis (fusion)
7. Hip arthrodesis (fusion)
8. Synovectomy
9. Other: _____

* For day surgeries, please input 0 days.

1023259 Real-World Impact of RA

Site number	-	Participant ID
-------------	---	----------------

4. Since you last filled out this questionnaire, when you visited the healthcare professional(s) for treatment of your rheumatoid arthritis, did you receive any Hylan G-F 20 (Synvisc) injection?

₀ No, consultation only

₁ Yes →

Injection Place

Number of shots

₁ Hip _____

₂ Knee _____

5. Since you last filled out this questionnaire, when you visited the healthcare professional(s) for treatment of your rheumatoid arthritis, did you receive any adalimumab (Humira)?

₀ No injection performed

₁ Yes →

Dosage

Times per month

_____ mg _____

If you have stopped using Adalimumab, when did you stop?

____/____/_____
(DD/MM/YYYY)

1023259 Real-World Impact of RA
[Site number] - [Participant ID]

6. Since you last filled out this questionnaire, have you taken any medications for your rheumatoid arthritis?			
Drug name	Average number of pills per day	Dose strength	Times per month
Disease Modifying Antirheumatic Drug (DMARD)			

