 - Age at baseline
 - Age groups
 - Gender at birth
 - Marital status (married, unmarried)
 - Medical plan type
 - ✓ The type of healthcare plan each patient is enrolled in at baseline will be determined, including National/Public insurance, Private insurance, Employer benefits, and Other
- **Clinical characteristics**
 - Initial Diagnosis of Rheumatoid Arthritis (RA)
 - ✓ Year of initial diagnose
 - Initiation of Adalimumab
 - ✓ First time administration (DD/MM/YYYY)
 - ✓ Dosage of first injection (in mg)
 - Disease status of RA
 - ✓ Moderate (defined as Disease Activity Score in 28 Joints (DAS28) between 3.2 and 5.1)
 - ✓ Severe (DAS28>5.1)
 - Erythrocyte sedimentation rate (ESR) (in mm/hour)
 - C reactive protein (CRP) (in mg/L)
 - Disease Activity Score in 28 joints (DAS28)

To calculate the DAS28, the physician or specialist nurse will:

1. Count the number of swollen joints (out of the 28)
2. Count the number of tender joints (out of the 28)
3. Take blood to measure the erythrocyte sedimentation rate (ESR) or C reactive protein (CRP); the latest measurement in the medical records may also be used if a blood draw is not standard for that visit

4. Ask the patient to make a 'global assessment of health' which will be indicated by marking a 10 cm line between very good and very bad

The physician or specialist nurse will then mark each component score on the CRF and the DAS28 score if calculated (an online scoring calculator for the DAS28 can be found at <http://www.das-score.nl/das28/DAScalculators/dascalculators.html>).

The DAS28 will be scored using the following formula:

$$\text{DAS28} = 0.56 * \text{sqrt}(\text{tender28}) + 0.28 * \text{sqrt}(\text{swollen28}) + 0.70 * \ln(\text{ESR or CRP}) + 0.014 * (\text{Global assessment of Health})$$

DAS28 scores will be interpreted using the following categorization:

- ✓ Remission: DAS28 \leq 2.6
- ✓ Low Disease Activity: $2.6 < \text{DAS28} \leq 3.2$
- ✓ Moderate Disease Activity: $3.2 < \text{DAS28} \leq 5.1$
- ✓ High Disease Activity: DAS28 > 5.1

– comorbidities

- ✓ Myocardial infarction
- ✓ Congestive heart failure
- ✓ Peripheral vascular disease
- ✓ Cerebrovascular disease
- ✓ Dementia
- ✓ Chronic pulmonary disease
- ✓ Connective tissue disease
- ✓ Ulcer disease
- ✓ Mild liver disease
- ✓ Diabetes
- ✓ Hemiplegia
- ✓ Moderate or severe renal disease
- ✓ Diabetes with end-organ damage
- ✓ Any tumor
- ✓ Leukemia
- ✓ Lymphoma
- ✓ Moderate or severe liver disease
- ✓ Metastatic solid tumor
- ✓ AIDS

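### The rule setting every missing day to the 15th has no bound from known dates, so it can date a post-baseline event before the first dose or a treatment stop after the form reporting it

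*SAP*

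**What the plan says.** SAP 3.5.5 rules out general imputation, allows item-level imputation of the patient-reported outcomes, and makes one further exception: "except with date data where the exact day is missing", in which case day 15 is assumed. It gives no earliest or latest permitted date and treats start and stop dates alike. The same paragraph says efficacy is not assessed after adalimumab is discontinued. Protocol 9.7.9 has no date rule, so the SAP governs alone.

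The dates that could bound an imputed day are already collected:

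- **First dose.** The baseline CRF (Protocol Appendix C, item 10) and SAP 3.5.2 take it as day, month and year. Inclusion criterion 4 (Protocol 9.2.1) requires that the patient "initiated adalimumab at baseline visit".
- **Stop.** The follow-up CRF (Appendix C, item 7) has a field "Administration stop date (if stopped"). The patient's follow-up questionnaire (Appendix J, item 5) asks "If you have stopped using Adalimumab, when did you stop". The Early Termination Forms (Appendix K) ask for it too.
- **Form date.** The CRFs, the resource-use questionnaires and the Early Termination Forms each carry a completion date.

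The analysis that most directly needs an order of dates is Protocol 9.7.7: "Adverse events occurring while participants are on adalimumab will be coded".

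**The concern.** A mid-month default is a common convention, but it is normally subject to what is already known. Without that limit, the rule can contradict a complete date in the same record. An event known to follow baseline can appear to precede treatment, and a stop can appear to follow the form that reported it. The rule itself creates these errors, even when every recorded date is right.

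At stake is mainly which adverse events fall in the on-adalimumab period of Protocol 9.7.7. A second route is the SAP 3.5.5 rule on efficacy after discontinuation. A third exists only if a programmer derives continuing or withdrawn status from an imputed stop date. Partial stop dates are plausible, because one source is patient recall over about three months.

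**Working it through.** The documents give no figure for this rule, so there is nothing to reproduce. The check is a count of dates.

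**Inputs.** Day 15 for any missing day, with no bound (SAP 3.5.5). Week 24 is day 168 after baseline (Protocol Table 1). Assumptions: a 30-day month, all days equally likely, and the month and year known and correct.

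**Worked example.** First dose on 20 January 2016; an event on 25 January with its day missing becomes 15 January, 5 days before treatment. The Week 24 visit falls on 20 January + 168 days = 6 July 2016. A true stop on 2 July with its day missing becomes 15 July, 9 days after the form that reports it.

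**Event in the first-dose month.** With first dose on day S, eligible event days are S to 30, which is 31 − S days. The imputed date precedes the first dose when S ≥ 16.
- Misplaced: sum of (31 − S) for S = 16 to 30 = 120
- All: sum of (31 − S) for S = 1 to 30 = 465
- Share: 120/465 = 25.8%

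**Stop in the month of a visit.** With the visit on day V, stops before it number V − 1. The imputed date follows the visit when V ≤ 14.
- Misplaced: sum of (V − 1) for V = 1 to 14 = 91
- All: sum of (V − 1) for V = 1 to 30 = 435
- Share: 91/435 = 20.9%

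**Event in the stop month, stop day T known.**
- Truly on or before the stop but dated after it (T ≤ 14): sum of T for T = 1 to 14 = 105, out of 465; 22.6%
- Truly after the stop but dated on or before it (T ≥ 15): sum of (30 − T) for T = 15 to 30 = 120, out of 435; 27.6%

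The last two shares act in opposite directions.

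**Calendar cross-check.** Baseline dates from 10 October 2015 to 16 August 2016 (31 January 2017 minus 168 days) give 312 dates. Day 15 of the baseline month precedes the first dose for 156 of them (50%). Allowing Week 24 visits at day 168 ± 7 gives 312 × 15 = 4,680 combinations. Day 15 of the visit month follows the visit in 2,127 (45%). Averaged over the possible true days, the shares are 26% for events and 21% for stops on or before the visit, in line with the 30-day grid.

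**Rough scale.** Suppose 13 stops (100 patients at the SAP section 4 drop-out of 13%), spread evenly over six months. If every day were missing, 13 × 1/6 × 0.21 = about 0.45 stops would be dated after the Week 24 visit. If 20% of days were missing, 0.45 × 0.2 = 0.09. The even spread and both missing rates are assumptions. Drop-outs who stay on adalimumab have no stop date, so 13 is on the high side.

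**The case against.** The strongest case against is that no planned table is shown to use an imputed date. Much of it stands.

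- **Continuing or withdrawn status.** A reader might infer that misdated stops move patients between the as-observed and withdrawal populations, and so count each misdated stop as a sizeable fraction of the withdrawal group. The documents do not support this. Neither derives status from a stop date. The follow-up CRF records injections since the last survey, with a stop date only if stopped. Protocol 12.6 sends patients switched off adalimumab to the Early Termination Form. A form that reports a stop already shows that the patient stopped, whatever day is imputed.
- **Timing limits.** A reader might set the size of the error against the instruction that "Terminal Visit data should be collected within 2 weeks of the last dose of adalimumab", or against the 7-day visit window. The first tells sites when to collect data and is not an analysis filter. The second governs form dates counted from baseline, not event dates. An imputed day removes no score under either.
- **Direction.** A reader might infer that the errors lead to under-reported adverse events. At the first-dose end they do run toward exclusion. At the stop end the wrongly included share (28%) exceeds the wrongly excluded share (23%). Collection runs to 70 days after the last dose (Protocol 11.1.4), so post-stop events are real candidates for inclusion.
- **Exposure to the rule.** The SAP's table list (section 6) has no adverse event table, and the forms in the appendices show no adverse event date field. Partial adverse event dates are therefore an assumption. The follow-up resource-use questions ask about the time since the last questionnaire and do not depend on the rule.
- **Safeguards.** Source document review for safety and post-entry logic checks (Protocol 9.8.2, SAP 3.3.4) could expose an impossible order. They are described for entered data, and neither says how an imputed date that fails a check is resolved.

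None of this supplies the missing bound. A stated rule that yields a wrong value when followed exactly is a defect, even if a minor one.

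**Conclusion.** The point holds as a minor one. SAP 3.5.5, followed as written, can date a post-baseline event before a known first dose, or a stop after the form that reports it. Within the boundary month and given a missing day, the shares are 26% and 21%. Around a stop date, 23% of on-treatment events are moved out and 28% of post-stop events are moved in, so the net direction is not established.

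These shares rest on uniform days and apply only to day-missing records in the boundary month. The documents give no count of such records, and the effect is probably small. It acts mainly through the adverse event summary in Protocol 9.7.7. It reaches continuing or withdrawn status only if that status were derived from an imputed stop date, which neither document says. No sample size, power or alpha figure changes.

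**What to change.** Amend SAP 3.5.5 as follows:

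1. Use day 15 only where it is consistent with known dates. Otherwise set the imputed date no earlier than the first dose (for stop dates and events known to be post-baseline) or the previous form, and no later than the date of the reporting form.
2. Count an adverse event with a missing day as on treatment unless its known month and year rule that out.
3. Take continuing or withdrawn status from the follow-up CRF or Early Termination Form entry, not from an imputed date.

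The bounds remove both impossible orders by construction, though not the uncertainty about the true day. The cost is a few sentences and minor programming, with no new data. The downside is small: a few more adverse events may count as on treatment, because a day-missing event in the stop month is counted even if it truly followed the stop.
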